APPENDIX F. RESHEATH AND RECAPTURE DEFINITIONS

The following definitions are applicable to the data elements on the Implant e-CRF that address the use of the resheath and recapture feature.

Resheath attempt	An attempt to intentionally resheath only a portion of the Evolut R TAV (including the frame) into the capsule of the delivery catheter (e.g. with the intent to reposition of the valve during deployment).
Recapture attempt	An attempt to intentionally fully resheath the entire Evolut R TAV (including the frame) into the capsule of the delivery catheter until there is no gap between capsule and the tip (e.g. with the intent to enable re-crossing of the aortic valve or retrieval of the system).
Point of no return	The point at which the capsule marker is aligned with the distal aspect of the spindle (Figure 14C).
Valve functionality	Functional valve performance is defined as the presence of stable systemic pressure (approximately > 80% of pre-implant mean arterial pressure).
Successful resheath attempt	Successful resheathing is defined as Evolut R TAV (including frame) was resheathed into the capsule of the delivery catheter to the desired amount intended, as verified by fluoroscopy.
Successful full recapture attempt	The entire Evolut R TAV (including the frame) is fully resheathed into the capsule of the delivery catheter until there is no gap between the capsule and the tip, as verified by fluoroscopy.

[figure not shown]

Figure 14. (A) Between 0 and 1/3 of the valve length outside of the capsule; (B) between 1/3 and 2/3 of the valve length outside of the capsule; (C) Point of no return: capsule marker in alignment with the spindle marker; (D) Full recapture: entire valve

APPENDIX G. EVENT CODE LIST

Myocardial Infarction

- 100 Peri-procedural myocardial infarction
- 101 Spontaneous myocardial infarction

Stroke and TIA

- 102 Disabling stroke: ischemic
- 103 Disabling stroke: hemorrhagic
- 104 Disabling stroke: undetermined origin
- 105 Non-disabling stroke: ischemic
- 106 Non-disabling stroke: hemorrhagic
- 107 Non-disabling stroke: undetermined origin
- 108 Transient ischemic attack

Bleeding Complications

- 110 Life threatening or disabling bleeding event
- 111 Major bleeding event
- 112 Minor bleeding event

Acute Kidney Injury

- 113 Acute kidney injury: stage 1
- 114 Acute kidney injury: stage 2
- 115 Acute kidney injury: stage 3

Vascular Access and Access Site Complications

Major

- 120 Major vascular complication: aortic dissection, aortic rupture, LV perforation, or new apical aneurysm/pseudoaneurysm
- 121 Major vascular complication: access site or access site-related vascular injury (dissection, stenosis, perforation, etc)
- 122 Major vascular complication: distal embolization from vascular source
- 123 Unplanned endovascular or surgical intervention
- 124 New ipsilateral lower extremity ischemia
- 125 Surgery for access site-related nerve injury
- 126 Permanent access site-related nerve injury
- 127 Other major vascular complication

Minor

- 130 Minor vascular complication: access site or access site-related vascular injury
- 131 Minor vascular complication: distal embolization from vascular source
- 132 Unplanned endovascular stenting or unplanned surgical intervention not meeting criteria for major complication
- 133 Vascular repair or need for vascular repair
- 134 Other minor vascular access site complication
- 140 Failure of closure device leading to alternative treatment

Other TAVI-Related Complications

- 150 Conversion to open surgery
- 151 Unplanned use of CPB
- 152 Coronary artery obstruction
- 153 Ventricular septal perforation
- 154 Mitral valve apparatus damage or dysfunction
- 155 Cardiac tamponade
- 156 Prosthetic valve thrombosis
- 157 Valve migration
- 158 Valve embolization
- 159 Ectopic valve deployment
- 160 TAV in TAV deployment
- 161 Major hemolysis
- 162 Minor hemolysis
- 163 Prosthetic valve endocarditis: definite
- 164 Prosthetic valve endocarditis: possible
- 165 Major frame fracture
- 166 Minor frame fracture
- 167 Other TAVI-related complication

Conduction Disturbances and Arrhythmias

- 170 Atrio-ventricular block, 1°
- 171 Atrio-ventricular block, 2°
- 172 Atria-ventricular block, 3°

- 173 LBBB
- 174 RBBB
- 175 Left anterior fascicular block
- 176 Left posterior fascicular block
- 180 Atrial fibrillation
- 181 Atrial flutter
- 182 Junctional rhythm (<100 bpm)
- 183 Junctional rhythm (≥100 bpm)
- 184 Sinus bradycardia (<50 bpm)
- 185 Supraventricular tachycardia
- 186 Ventricular fibrillation
- 187 Ventricular premature beats
- 188 Ventricular tachycardia
- 189 Other arrhythmia

Prosthetic Valve Dysfunction

- 190 Mild stenosis
- 191 Moderate/severe stenosis
- 192 Moderate paravalvular regurgitation
- 193 Severe paravalvular regurgitation
- 194 Moderate transvalvular regurgitation
- 195 Severe transvalvular regurgitation

Other Implantation/Catheterization Procedure-Related Adverse Events

- 200 Brachial plexus injury
- 201 Hypovolemia
- 202 Hypotension requiring intervention
- 203 Air embolism
- 204 Venous thrombosis, definite
- 205 Venous thrombosis, suspected
- 206 Metabolic acidosis
- 207 Catheter induced arrhythmia
- 208 Hemothorax
- 209 Radiation-induced erythema
- 210 Other implantation/catheterization

Other Cardiac Adverse Events

- 300 Cardiac arrest
- 301 Congestive heart failure
- 302 Cardiogenic shock
- 303 Valvular regurgitation, mitral
- 304 Valvular regurgitation, tricuspid
- 307 Syncope
- 308 Palpitations
- 309 Cyanosis
- 310 Chest pain
- 311 Pericardial effusion, hemorrhagic
- 312 Pericardial effusion, non-hemorrhagic
- 313 Intracardiac mass
- 399 Other cardiac event

Respiratory/Pulmonary Adverse Events

- 400 Respiratory arrest
- 401 Pneumothorax
- 402 Chronic pulmonary disease
- 403 Bronchospasm/asthma
- 404 Pleural effusion
- 405 Hemoptysis
- 406 Respiratory failure
- 407 Atelectasis
- 408 Hemothorax
- 409 Respiratory insufficiency
- 410 Apnea/hypoventilation
- 499 Other respiratory/pulmonary

Other Neurologic Adverse Events

- 500 Seizure(s)
- 502 Meningitis, infectious
- 504 Headaches
- 505 Dizziness
- 599 Other central nervous system

Gastrointestinal Adverse Events

600 Vomiting
601 Diarrhea
602 Protein losing enteropathy
603 Liver disease
604 Liver failure
699 Other gastrointestinal

1002 Rash
1003 Contrast reaction/allergy
1004 Medication reaction/allergy
1099 Other allergic reaction

Other

1200 Multi organ failure
1299 Other

Hematologic/Oncologic Adverse Events

700 Cancer/malignancy
701 Coagulopathy
702 Anemia (Hgb <10g or Hct <30%)
703 Thrombocytopenia
704 Transfusion reaction
799 Other hematologic/oncologic

Infection Adverse Events

801 Fever ($\geq 39.0^{\circ}\text{C}$)
802 Sepsis, confirmed (positive blood culture)
803 Sepsis, suspected (by clinical findings)
804 Endocarditis, other than Evolut R
805 Urinary tract infection
806 Pneumonia
807 Gastroenteritis
808 Hepatitis
809 Upper respiratory tract infection
899 Other infection

Other Renal Adverse Events (Exclusive of AKI)

900 Renal insufficiency
902 Chronic renal failure
903 Proteinuria
904 Urinary retention
999 Other renal

Allergic Reactions

1000 Anaphylaxis
1001 Pruritus

08 DEC 2015

Prepared by:

[name] PH.D

Principle Statistician

Copyright © 2015 by Medtronic

Approvals

The undersigned have reviewed this document and agree with its contents.

[name], Study Biostatistician

Date

[name], Sr. Biostatistics Manager

Date

[name], Clinical Research Manager

Date

TABLE OF CONTENTS

Approvals	2
1. Introduction / Purpose of SAP	4
2. Study Design	4
3. Description of Analyses	5
3.1. General Summaries	5
3.2. Baseline Characteristics	5
3.3. Handling of Dropouts and Missing Data	5
3.4. Analysis Sets	5
3.5. Kaplan-Meier Analyses	6
3.6. Primary Objective	6
3.7. Secondary Objectives	8
3.8. Interim Analysis	10
4. Revision Process	10
5. Revision History	10

1. Introduction / Purpose of SAP

This document outlines the detailed statistical methods to be implemented for the data collected within the scope of the Medtronic Coronary and Structural Heart (CSH) CoreValve™ Evolut R™ FORWARD clinical study. The purpose of this plan is to provide a framework which answers the study objectives in a statistically rigorous fashion, without bias or analytical deficiencies.

Specifically, the Plan has the following purpose: to prospectively (a priori) outline the types of analyses and presentations of data that will form the basis for conclusions to be reached that will answer the study objectives outlined in the protocol, and to explain in detail how the data will be handled and analyzed, adhering to commonly accepted standards and practices of statistical analysis in the medical device industry.

This Statistical Analysis Plan applies to the study final report. This SAP also applies to the main study manuscript, though not everything specified here will be included in the manuscript.

2. Study Design

The study objective is to document the clinical and device performance outcomes of the Evolut R system used in routine hospital practice in a large patient cohort for the treatment of symptomatic native aortic valve stenosis or a stenosed, insufficient, or combined surgical bioprosthetic valve failure necessitating valve replacement.

This is a prospective, single arm, multi-center, observational, post market study. In Australia and Canada it is a prospective, single arm, multi-center pre-market study. Approximately 1000 subjects implanted with the Evolut R system will be included. Subjects will be followed at 30 days, 1, 2 and 3 years after the procedure. Based on clinical assessments during the course of the study, follow up may be extended to up to 5 years post procedure.

Enrollment parameters are included in the study to avoid introduction of bias to the trial results due to disproportionate enrollment. Enrollment shall not exceed 7.5% (75 patients) of the total implanted patients at any individual site. In addition, enrollment shall not exceed 40% (400 patients) of the total implanted patients at any individual country.

Enrollment will be competitive across sites. The per-site and per-country enrollment cap may be increased upon Sponsor approval. There is no set minimum number of patients to be enrolled per site; however there is an expected minimum enrollment of 15 subjects per site.

At the time when the study-wide enrollment cap of 1000 implanted subjects has been reached, further enrollment into the study will cease regardless of whether individual sites have reached their per-site cap.

The study methods include the following measures to minimize potential sources of bias:

- An external, independent Clinical Events Committee (CEC) will review and adjudicate, at minimum, all deaths and safety endpoint related adverse events. Safety endpoint results will be based on CEC adjudications.
- All sites will follow a standardized protocol for acquisition of echocardiographic endpoint data.
- An Echo Core Lab will evaluate all echocardiograms. Echocardiographic study endpoint results will be based on Core Lab assessments.
- Study sites should follow their institutional procedures for maintenance of echocardiography and laboratory equipment used for assessing the study variables.
- Study monitors will verify patients' data and ensure compliance with the Clinical Investigational Plan and other study requirements.

Subject selection criteria are based on the Instructions for Use of the Evolut R System.

Inclusion Criteria

- Symptomatic native aortic valve stenosis or a stenosed, insufficient, or combined surgical bioprosthetic valve failure necessitating valve replacement

- Acceptable candidate for elective treatment with the Evolut R System and in conformity with the local regulatory and medico economic context
- Age ≥ 80 years OR considered to be at high or greater risk for surgical aortic valve replacement (AVR) where high risk is defined as:
 - Society of Thoracic Surgeons (STS) predicted risk of mortality $\geq 8\%$
 - OR
 - Documented heart team agreement of risk for AVR due to frailty or comorbidities
- Geographically stable and willing to return to the implanting site for all follow-up visits
- Of legal age to provide informed consent (patient Informed Consent or Data Release Form) in the country where they enroll in the trial
- The patient has been informed of the nature of the study, is able and willing to provide consent without assistance from a legal representative and has consented to participate, and has authorized the collection and release of his/her medical information by signing a Patient Informed Consent or Data Release Form.

Exclusion Criteria

- Known hypersensitivity or contraindication to aspirin, heparin (HIT/HITTS) and bivalirudin, ticlopidine, clopidogrel, Nitinol (Titanium or Nickel), or sensitivity to contrast media, which cannot be adequately premedicated
- Preexisting mechanical heart valve in aortic position
- Ongoing sepsis, including active endocarditis
- Anatomically not suitable for the Evolut R system
- Estimated life expectancy of less than 1 year
- Participating in another trial that may influence the outcome of this trial
- Need for emergency surgery for any reason

3. Description of Analyses

3.1. General Summaries

All continuous variables will be summarized with means, medians, standard deviations, minimums, and maximums. Categorical variables will be summarized with frequencies and percentages.

3.2. Baseline Characteristics

Baseline demographic and clinical variables will be summarized for the attempted implant analysis set (safety set) as defined in section 3.4.

3.3. Handling of Dropouts and Missing Data

Every effort will be undertaken to minimize missing data. In time-to-event outcomes drop-outs will be censored at the time of discontinuation, consistent with the Kaplan-Meier approach.

Unless otherwise specified in each objective, no statistical techniques will be used to impute missing data for continuous or categorical outcomes. If a subject's data are missing for any reason, that subject will not be included in that portion of the analysis. The number of subjects included in each analysis will be reported so that the reader can assess the potential impact of missing data.

In the case of partial dates, if only the month and year are known, the event or assessment will be analyzed as if it occurred on the 15th of that month. If only the year is known, the event or assessment will be analyzed as if it occurred on June 30th of that year. These resolutions of partial dates are subject to the restrictions that pre-procedure events and assessments must occur between the enrollment date and the procedure date and post-procedure events and assessments must occur no earlier than the procedure date.

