2.5 Number of investigation sites and study duration

The study will be a multicenter, multinational study conducted at up to 60 investigational sites. These centers may be located in Europe, Middle East and Africa, Latin America, Australia and Canada. Other regions may be added depending on the regulatory status of the device. At the time this Clinical Investigation Plan was finalized not all participating investigation sites were identified. A list of participating investigation sites which includes the name and title of the investigator(s) who is (are) responsible for conducting the trial, and the address and telephone number(s) of the trial site(s). They will be submitted under a separate cover and will be available in the Investigator Site File.

It is anticipated that enrollment will take approximately 18 months. As each implanted subject is to be followed for three years, the estimated study duration is approximately 54 months, excluding the time required for preparing the final report. If each subject will be followed for 5 years, the estimated study duration is approximately 78 months.

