5.2.5 Follow-up Visits

Patients are followed per standard of care. Information from visits performed at the implanting hospital should preferably be used for the follow-up visits. If the patient did not return to the implanting hospital, but was followed at a local hospital, this information can be used as an alternative. If no hospital visit occurred, a telephone follow-up visit can be performed.

5.2.6 30 days

There are no mandatory visit windows defined in this study; however it is recommended that the 30-day follow up visit should occur between 30 and 60 days post procedure.

- NYHA functional classification
- 12-lead ECG
- Physical Examination
- Relevant medication use.
- Modified Rankin Score (mRS)
- Review of relevant adverse events and device deficiencies (see section 5.7 for requirements)

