3.6.2. Primary Endpoint Definition

The primary endpoint is the binary rate of all-cause mortality at 30 days post procedure. The numerator will be the number of subjects who died on or before 30 days post procedure, and the denominator will be the number of subjects in the safety set (defined in section Analysis Sets 3.4) who died on or before 30 days post procedure, or whose latest date of all follow-up visits, assessments, and events is at least 30 days post procedure.

In addition, the KM event rates for all-cause mortality at 30 days, 1 year, 2 years and 3 years, as well as the KM plot will be provided.

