3.6.5. Data Collection and Analysis Methods

Death data will be collected on a separate site death case report form. All-cause death events will be adjudicated by the CEC. And the data on the CEC death adjudication form will be used in the analysis.

The all-cause mortality rate at 30 days post procedure will be compared with the performance goal of 10%, with a one-sided Fisher exact test at the 0.05 significance level. The analysis for this objective will be based on the safety set.

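### The partial-date rule in SAP 3.3 is bounded only by the procedure date, so a death can be dated before a visit at which the subject was documented alive, and across day 30; few records should be affected.

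*SAP*

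**What the plan says.** SAP 3.3 gives two rules for dates that are incomplete: "if only the month and year are known, the event or assessment will be analyzed as if it occurred on the 15th of that month", and "If only the year is known, the event or assessment will be analyzed as if it occurred on June 30th of that year". Its only restriction on the post-procedure side is that "post-procedure events and assessments must occur no earlier than the procedure date". The rules cover events and assessments alike, with no exception for death.

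SAP 3.6.2 defines the primary endpoint by date: "The numerator will be the number of subjects who died on or before 30 days post procedure". Subjects not counted as 30-day deaths enter the denominator if they are people "whose latest date of all follow-up visits, assessments, and events is at least 30 days post procedure".

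SAP 3.6.5 names the source of the death data: "And the data on the CEC death adjudication form will be used in the analysis". It does not say how a partial date on that form is resolved. SAP 3.5 uses the last contact only to censor subjects without an event. The sensitivity analyses in SAP 3.6.6 concern missing outcomes, and a partially dated death is not missing once it has been given a date. The protocol has no partial-date rule.

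**The concern.** The endpoint depends on which side of day 30 a death falls, yet the imputation ignores the evidence in the subject's own record that bears on this. A contact at day 30 or later is what makes a survivor evaluable under SAP 3.6.2. Under SAP 3.3, a subject with that same contact can be dated as dying before it.

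Such contacts will be common, because "it is recommended that the 30-day follow up visit should occur between 30 and 60 days post procedure" (Protocol 5.2.6). Incomplete death dates are conceivable, since follow-up may be taken from a local hospital or by telephone (Protocol 5.2.5) and vital status is sought after loss to follow-up (Protocol 5.4.2).

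The same rule supplies dates for the Kaplan-Meier mortality rates to 3 years (SAP 3.6.2) and for the 30-day safety and pacemaker rates (SAP 3.7.3.4 and 3.7.4.4). There too an event could be placed before a contact at which the subject was event-free.

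**Working it through.** **Inputs.** Date rules and bound: SAP 3.3. Numerator and denominator: SAP 3.6.2. Performance goal 10.0%, expected rate 7.3%, one-sided alpha 0.05, 934 evaluable subjects raised to 1000: SAP 3.6.4. Visit window of days 30 to 60: Protocol 5.2.6. Calendar dates below are illustrative.

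**1. The plan's own figure.** The exact one-sided binomial test passes with at most c deaths, where c is the largest value with P(X ≤ c | n, 0.10) ≤ 0.05. Power is P(X ≤ c | n, 0.073).
- n = 934: c = 78, alpha 0.0493, power 0.901. The stated 934 for 90% power is reproduced.
- n = 1000: c = 84 (p = 0.0485); 85 deaths fail (p = 0.0607). Power is 0.917.

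**2. Single records.** Imputed day = imputed date minus procedure date. The death counts if this is 30 or less.
- Month known: procedure 16 March, alive 20 April (day 35), death known only as April. Imputed 15 April = day 30, so counted.
- Year known: procedure 10 June, alive 15 July (day 35), death later that year. Imputed 30 June = day 20, so counted.
- Opposite direction: procedure 15 January 2016, true death within 30 days, only the year known. Imputed 30 June = day 167, so not counted. Because SAP 3.6.2 includes events in the latest date, the imputed date itself makes this subject an evaluable survivor.

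None of these needs any interpretation of the restriction.

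**3. Procedure dates exposed under the year-only rule.** For procedures from 31 May to 30 June (31 dates), a later death in the same year is imputed to days 0 to 30 directly. For 1 July to 30 November (153 dates), 30 June precedes the procedure. The death counts only if a violating date is moved up to the procedure date, which the SAP does not say. Together that is 31 + 153 = 184 dates, half the year.

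**4. Share of partially dated deaths moved** (all procedure dates over three years, deaths spread evenly over the days shown)

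| | Month only | Year only |
|---|---|---|
| True day 31–60, moved in | 13.9% | 46.4% (8.5% without the reset) |
| of all such deaths: moved in and contradicting a contact after day 30 | about 3% | about 23% (about 4% without the reset) |
| True day 0–30, moved out | 11.1% | 45.3% |

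The second row assumes one visit, uniform over days 30 to 60 and allowed up to the day of death, with no other contacts. Requiring the visit before the day of death gives about 2% and 21%.

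**5. Effect on the test at n = 1000, true rate 7.3%.** The expected count is 73, which is 11 below the limit of 84.
- One added death changes pass to fail only if the true count is 84: P(X = 84) = 0.019.
- Five added deaths: P(80 ≤ X ≤ 84) = 0.13.
- In the other direction, at a true rate of exactly 10.0%, losing one true death from the count in every trial would raise the false-success probability from 0.0485 to 0.0607.

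**The case against.** The strongest reply is that incomplete dates for early deaths should be rare and would tend to be caught. A death is a serious adverse event, reportable within 5 calendar days of site knowledge, or 24 hours in Australia (Protocol 5.7.5), with dates of onset and of site awareness recorded (Protocol 5.7.2). Every death is adjudicated (Protocol 5.7.7), endpoint data are checked against medical records (Protocol 6.2), and the database runs logic checks (Protocol 6.1.3). A year-only date for a death within 60 days of an elective implant would be extreme. This stands, and it keeps the point small. It does not supply the missing bound: none of these controls says which date to analyse once it is incomplete.

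Three stronger readings are tempting, and the documents do not support them.
- A reader might take 14% and 46% as the share of late deaths that contradict a documented contact. Those figures cover all partially dated deaths on days 31 to 60, seen alive after day 30 or not. The share with a contradicting contact is about 3% and 23% under the visit assumption above.
- A reader might conclude that any year-only death after a July to November procedure lands on day 0. About 38 of the 46 percentage points rest on that reset, which SAP 3.3 does not state.
- A reader might infer that the primary conclusion is fragile because 84 deaths pass and 85 fail. Every exact test has such an edge; at 7.3% the expected count is well below it.

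**Conclusion.** The defect is real but small. Followed as written, SAP 3.3 can date a death before documented evidence of life and put a subject known to be alive after day 30 into the 30-day numerator. No other section of the SAP or protocol prevents this.

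That error raises observed mortality, so it cannot create a false success. The reverse error, a true 30-day death dated later, favours the sponsor and comes from the same rule.

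A changed primary conclusion is unlikely: about 2% for one added death and about 13% for five, at n = 1000 and a true rate of 7.3%. The assumed range of 0 to 5 partially dated deaths is not from the documents. The five-death figure also supposes that every such record is misdated inward. The case for changing the text is that a stated rule gives a demonstrably wrong date when the data to avoid it are at hand.

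**What to change.** In SAP 3.3, add that an imputed post-procedure event date may be no earlier than the last documented contact at which the subject was alive (or, for other events, event-free) and no later than the date the site became aware. Within those bounds and the known month or year, use the midpoint. If awareness came no earlier than the end of the known month or year, the first two examples become:
- 20 to 30 April, midpoint 25 April = day 40;
- 15 July to 31 December, midpoint 7 October = day 119.

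Both leave the 30-day numerator.

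In SAP 3.6.6, add that any death whose permitted interval still spans day 30 is reported both ways: once as a 30-day death and once not. Such deaths should not all be forced into the numerator of the primary analysis. That is a debatable conservative choice, and it can add to the inward misclassification the bounds are meant to reduce.

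The cost is a few sentences in the SAP and a small addition to an existing sensitivity analysis. Contact dates are already used in SAP 3.5 and 3.6.2, and the awareness date is on the adverse event form (Protocol 5.7.2). No new data are needed and the sample size is unchanged.
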